1.4.1.2 Infections

Fatal and non-fatal infections have occurred with ibrutinib therapy. Grade 3 or greater infections occurred in 14% to 26% of patients. Cases of progressive multifocal leukoencephalopathy (PML) have occurred in patients treated with ibrutinib. Monitor patients for fever and infections and evaluate promptly.

1.4.1.3 Cytopenias

Treatment-emergent Grade 3 or 4 cytopenias including neutropenia (range, 19 to 29%), thrombocytopenia (range, 5 to 17%), and anemia (range, 0 to 9%) occurred in patients treated with ibrutinib.

1.4.1.4 Atrial Fibrillation

Atrial fibrillation and atrial flutter (range, 6 to 9%) have occurred in patients treated with ibrutinib, particularly in patients with cardiac risk factors, acute infections, and a previous history of atrial fibrillation. Periodically monitor patients clinically for atrial fibrillation. Patients who develop arrhythmic symptoms (e.g., palpitations, lightheadedness) or new onset dyspnea should have an ECG performed. If atrial fibrillation persists, consider the risks and benefits of ibrutinib treatment and dose modification.

1.4.1.5 Second Primary Malignancies

Other malignancies (range, 5 to 14%) including non-skin carcinomas (range, 1 to 3%) have occurred in patients treated with ibrutinib. The most frequent second primary malignancy was non-melanoma skin cancer (range, 4 to 11%).

1.4.1.6 Tumor Lysis Syndrome

Tumor lysis syndrome has been reported with ibrutinib therapy. Monitor patients closely and take appropriate precautions in patients at risk for tumor lysis syndrome (e.g. high tumor burden).

In the recently published long-term follow-up for patients with MCL treated with single agent ibrutinib, the following recurrent serious adverse events were reported:

Table 1-1 Ibrutinib: Recurrent Serious Adverse Events

SAE*, n (%)	Total (N=111)		
	Any Grade	Grade 3-4	Grade 5
Disease Progression	11 (10%)	3 (3%)	8 (7%)
Pneumonia	8 (7%)	7 (6%)	1 (1%)
Atrial Fibrillation	7 (6%)	6 (5%)	0
Urinary Tract Infection	4 (4%)	3 (3%)	0
Febrile Neutropenia	3 (3%)	3 (3%)	0
Abdominal Pain	3 (3%)	3 (3%)	0
Acute Renal Failure	3 (3%)	2 (2%)	1 (1%)
Subdural hematoma	3 (3%)	2 (2%)	0
Pyrexia	3 (3%)	1 (1%)	0
Confusional State	3 (3%)	1 (1%)	0

1.5 Summary of Rationale for Proposed Study**1.5.1 Rationale**

Single agent therapy for patients with relapsed MCL can result in responses that are durable for some patients but is not curative. With continued follow-up, it is evident that most patients will relapse within 2 years. As a result, we plan to build upon the successes of recently identified novel therapies by investigating a novel, all oral combination of ixazomib and ibrutinib. These agents appear to have synergy in pre-clinical assessments, as ibrutinib appears to result in increased cell death for MCL cells that are previously bortezomib-resistant when they are exposed to the combination.³³

While bortezomib is effective as a single agent in several settings in MCL, it is associated with dose-limiting peripheral neuropathy and also requires serial injections. Ixazomib is available orally and appears to have decreased peripheral

neuropathy, allowing for an all oral therapy for patients with relapsed MCL. As a result, we will proceed with a phase I/II study of ixazomib and ibrutinib in combination for relapsed/refractory mantle cell lymphoma. The phase I portion of the study will be designed to identify the appropriate dose of ixazomib when combined with ibrutinib in this setting, and the phase II portion of the study will assess the efficacy of this combination.

1.5.2 Rationale for the Study Design and Treatment Plan

We have elected to enroll both BTK-pretreated and BTK-naïve patients for this study. For the phase I portion of the study, which is focused primarily on safety and tolerability, all patients will be enrolled regardless of prior ibrutinib exposure. However, we will require ibrutinib pre-treated patients to satisfy specific criteria (Eligibility Criteria 3.4) in order to avoid rapid progression during the first cycle of therapy which would make dose limiting toxicity assessment challenging.

Phase I Summary: Three patients were enrolled to Dose Level 1 with no DLTs during the 28 day assessment period. Nine patients were enrolled to Dose Level 2, five of the nine patients completed the 28 day assessment period with no DLTs. One patient experienced a grade 3 lung infection that was considered a DLT. Three of the nine patients were not evaluable for DLT and were replaced. One patient was inadvertently given neulasta prior to receiving Cycle 2, Day 1 therapy; another patient unintentionally took Day 15 ixazomib on Day 9; and one patient forgot to take ibrutinib the last 8 days of Cycle 1 unrelated to any toxicities. The Phase I portion of the study was completed November 25, 2019. Dose Level 2 is the recommended Phase 2 dose with ixazomib 4 mg on Days 1, 8 and 15 of a 28 day cycle and ibrutinib 560 mg on Days 1-28 of a 28 day cycle.

For the phase II portion of the study, we have developed two dosing cohorts (BTK-pretreated and BTK-naïve), so that we can assess the efficacy of this combination in both settings. Based on the preclinical evidence of synergy, it is our hope and expectation that patients who have previously progressed on single agent ibrutinib or other BTK inhibitor will still achieve benefit when they receive the combination. Efficacy will be assessed separately for each cohort, with success determined based on historical cohorts. For BTK-pretreated patients, we will use the previously reported CR rate for bortezomib, while for BTK-naïve patients we will compare our results to the previously reported single agent activity of ibrutinib, using CR rate as the primary endpoint.

August 7, 2020: Phase II opened December 17, 2019 with Cohort A: BTK-naïve or Cohort B: BTK-pretreated.

Enrollment to Cohort A: BTK-naïve will continue. We plan to reach our original accrual goal of 36 BTK-naïve subjects treated at the established Dose Level 2 for 31 eligible, treated patients. The Phase I BTK-naïve patients treated at Dose Level 2 will be included in the 36 patient total. Seventeen additional BTK-naïve patients will be enrolled to complete this cohort.

Enrollment to Cohort B: BTK-pretreated will close. To date, only two patients have enrolled in Cohort B.

2. Study Objectives

2.1 Primary Objective

2.1.1 Phase I

To determine the maximum tolerated dose (MTD) of ixazomib in combination with ibrutinib in patients with relapsed/refractory mantle cell lymphoma (MCL).

2.1.2 Phase II

To determine the complete response (CR) rate of ixazomib in combination with ibrutinib in relapsed/refractory MCL in BTK-naïve patients.

2.2 Secondary Objectives

2.2.1 Phase I

- To evaluate regimen-related toxicities for the combination of ixazomib and ibrutinib in relapsed/refractory MCL.
- To evaluate preliminary evidence of efficacy by describing the overall response rate (ORR) for the combination.
- To evaluate evidence of efficacy by describing the median progression-free (PFS) and overall survival (OS) for patients treated with this combination.

2.2.2 Phase II

- To evaluate the ORR of the combination of ixazomib and ibrutinib.
- To evaluate PFS and OS for patients treated with the combination.
- To further evaluate regimen-related toxicity for patients treated with ixazomib and ibrutinib.

2.3 Exploratory Objectives

3. Selection of Patients

Each of the criteria in the checklist that follows must be met in order for a patient to be considered eligible for this study. Use the checklist to confirm a patient's eligibility. For each patient, this checklist must be photocopied, completed and maintained in the patient's chart.

In calculating days of tests and measurements, the day a test or measurement is done is considered Day 0. Therefore, if a test is done on a Monday, the Monday four weeks later would be considered Day 28.

PrECOG Patient No. _____

Patient's Initials (F, M, L) _____

Physician Signature and Date _____

NOTE: PrECOG does not allow waivers to any protocol specified criteria. All eligibility criteria listed in Section 3 must be met, without exception. The registration of individuals who do not meet all criteria listed in Section 3 can result in the participant being censored from the analysis of the study, and a major protocol violation. All questions regarding clarification of eligibility criteria must be directed to the Medical Monitor or PrECOG Study Contact.

NOTE: Institutions may use the eligibility checklist as source documentation if it has been reviewed, signed, and dated prior to registration by the treating physician.

_____ 3.1 Patients must have relapsed or refractory, pathologically proven mantle cell lymphoma. Patients must have a current or prior tissue sample that is IHC positive for cyclin D 1 or that is positive by FISH or cytogenetics for t(11;14).

Date of Relapse/Refractory MCL: _____

_____ 3.2 Patients must have been refractory to and/or relapsed/progressed after at least 1 prior therapy.

Date of Last Therapy: _____

_____ 3.3 Prior autologous or allogeneic transplant are allowed. Patients may not have active grade II-IV acute GVHD or moderate/severe chronic GVHD by NIH criteria and may not require immunosuppressive medications and/or corticosteroids for the management of acute or chronic GVHD.

_____ 3.4 **Phase I:** Prior proteasome inhibitor and/or Bruton's tyrosine kinase inhibitors are allowed but patients may not have been exposed to the combination of proteasome inhibitor and BTK inhibitor. Patients who have progressed on ibrutinib that are felt to be at high risk for rapid progression on this study shall not be eligible for the phase I portion of the study.
NOTE: Ibrutinib pre-treated patients must meet all eligibility criteria AND must have discontinued prior ibrutinib at least 3 months prior to starting study therapy.

Pretreated with ibrutinib: Yes No

If yes, does patient meet criteria above: Yes No

PHASE I COMPLETED NOVEMBER 25, 2019.

Phase II: Prior proteasome inhibitors allowed.

(Please note prior to Version 3.0 of the protocol prior proteasome inhibitor and/or Bruton's tyrosine kinase inhibitors were allowed but patients could not have been exposed to the combination of proteasome inhibitor and BTK inhibitor).

_____ 3.5 Age ≥ 18 years.

____ 3.6 ECOG performance status of 0-2 (Appendix I).

____ 3.7 Ability to understand and willingness to sign IRB-approved informed consent.

____ 3.8 Willing to provide archived tumor tissue, bone marrow (if sufficient bone marrow and tumor tissue are available) and blood samples for research (Section 13.0).

____ 3.9 Adequate organ function as measured by the following criteria, obtained \leq 2 weeks prior to registration:

- Absolute Neutrophil Count (ANC) \geq 750/mm³
ANC: _____ Date of Test: _____
- Platelets $>50,000/\text{mm}^3$
Platelets: _____ Date of Test: _____

NOTE: Platelet transfusions are not allowed within 3 days before registration to meet eligibility criteria.

- Serum Creatinine \leq 2x Upper Limit Normal (ULN)
Serum Creatinine: _____ ULN: _____ Date of Test: _____
- ALT and AST \leq 3x ULN
ALT: _____ Institution ULN: _____ Date of Test: _____
AST: _____ Institution ULN: _____ Date of Test: _____
- Total Bilirubin \leq 1.5x ULN (in the absence of previously diagnosed Gilbert's disease)
Total Bilirubin: _____ ULN: _____ Date of Test: _____

____ 3.10 Patients must not have received systemic treatment for MCL for at least 14 days prior to enrollment, except for steroids which may be used to manage acute symptoms related to disease up to 48 hours prior to starting study therapy. Radiation therapy must be concluded at least 14 days prior to enrollment.

____ 3.11 Women must not be pregnant or breastfeeding since we do not know the effects of ixazomib and ibrutinib on the fetus or breastfeeding child. All sexually active females of childbearing potential (not surgically sterilized and between menarche and 1 year post menopause) must have a blood test to rule out pregnancy within 2 weeks prior to registration.

Is the patient a woman of childbearing potential? _____ (yes/no)

If yes, Date of Test: _____ Results: _____

____ 3.12 Sexually active women of child-bearing potential with a non-sterilized male partner and sexually active men must agree to use 2 methods of adequate contraception (hormonal plus barrier or 2 barrier forms) OR abstinence prior to study entry, for the duration of study participation, and for 3 months following last dose of study drugs.

NOTE: Should a woman become pregnant or suspect she is pregnant while participating in this study, she should inform her treating physician immediately.

____ 3.13 Patients must have resolved all prior non-hematologic toxicities assessed as related to prior therapy to \leq grade 1.

____ 3.14 Patients must have measurable disease (i.e., \geq 1.5 cm in largest diameter) by conventional imaging modalities. Patients with extranodal involvement as the only measurable site of disease must have a largest diameter greater than \geq 1.0 cm and must be attributable to active lymphoma in the opinion of the investigator.

_____ 3.15 Patients may not have current/active Central Nervous System (CNS) involvement with mantle cell lymphoma (patients with prior CNS involvement are eligible as long as they have had no evidence of active CNS disease for at least 6 months). Patients without clinical evidence of CNS involvement do not require CNS assessment at screening.

_____ 3.16 Patients may not have another malignancy that could interfere with the evaluation of safety or efficacy of this combination. Patients with a prior malignancy will be allowed without study chair approval in the following circumstances:

- 1) Not currently active and diagnosed at least 3 years prior to the date of enrollment.
- 2) Non-invasive diseases such as low risk cervical cancer or any cancer in situ.
- 3) Localized disease in which chemotherapy would not be indicated (such as Stage I colon, lung, prostate or breast cancer). Patients with other malignancies not meeting these criteria must be discussed with PrECOG prior to enrollment.

_____ 3.17 Patients requiring long-term anticoagulation must be managed on an anticoagulant besides warfarin. Patients who require warfarin are not eligible.

_____ 3.18 Patients with a clinically significant bleeding episode as judged by the investigator within 3 months of registration are not eligible, except patients who suffer bleeding due to trauma.

_____ 3.19 Patients may not have had major surgery within 14 days, or minor surgery within 3 days, before registration.

_____ 3.20 Patients may not have any active infection requiring oral or intravenous antimicrobial therapy at the time of therapy initiation. Patients with a recent self-limited infection that has clinically resolved may complete a prescribed course of antimicrobial therapy after study initiation as long as they are asymptomatic with no clinical evidence of infection for at least 7 days prior to treatment. Patients with a recent serious (grade ≥ 3) infection requiring hospitalization must have completed all antimicrobial therapy within 14 days of therapy initiation.

_____ 3.21 Patients may not have evidence of uncontrolled cardiovascular conditions, including uncontrolled hypertension, uncontrolled cardiac arrhythmias, symptomatic congestive heart failure (NYHA class III or higher [Appendix II]), unstable angina, or myocardial infarction within the past 6 months. Patients with a history of any significant cardiovascular disease that has been controlled for at least 14 days before registration are allowed (except for patients who have had a myocardial infarction within 6 months).

_____ 3.22 No systemic treatment, within 14 days before the first dose of ibrutinib with moderate or strong inhibitors of CYP3A (Strong Inhibitors: ketoconazole, itraconazole, voriconazole, posaconazole, clarithromycin, and telithromycin; Moderate Inhibitors: fluconazole, darunavir, erythromycin, diltiazem, atazanavir, aprepitant, amprenavir, fosamprenavir, crizotinib, imatinib, verapamil, ciprofloxacin, grapefruit juice products, and Seville oranges) or strong CYP3A inducers for ibrutinib and ixazomib (carbamazepine, rifampin, phenytoin, St. John's wort). Refer to Section 11.2.7 for additional excluded medications and information.

_____ 3.23 Patients with ongoing or active systemic infection, active hepatitis B or C virus infection, or known Human Immunodeficiency Virus (HIV) positive are not eligible. Testing is not required in absence of clinical suspicion.

_____ 3.24 Patients with a history of hepatitis B or C must have a negative peripheral blood Polymerase Chain Reaction (PCR) and may not be positive for Hepatitis B surface antigen. Patients with cirrhosis or other evidence of liver damage due to Hepatitis B or C are not eligible.

_____ 3.25 Patients with any serious medical or psychiatric illness that could, in the investigator's opinion, potentially interfere with the completion of the treatment according to the protocol are not eligible.

- _____ 3.26 Patients with a known allergy to any of the study medications, their analogues, or excipients in the various formulations of any agent are not eligible.
- _____ 3.27 Patients with known GI disease or prior GI procedure that could interfere with the oral absorption or tolerance of ixazomib or ibrutinib including difficulty swallowing are not eligible.
- _____ 3.28 Patients with \geq Grade 2 peripheral neuropathy, or Grade 1 peripheral neuropathy with pain on clinical examination during the screening period are not eligible.
- _____ 3.29 Patients may not participate in any other therapeutic clinical trials, including those with other investigational agents not included in this trial throughout the duration of this study.
- _____ 3.30 As ibrutinib will not be provided by the study, the patient must be able to obtain ibrutinib through other means (i.e., commercially or through patient assistance programs). This must be confirmed prior to registration.

4. Registration Procedures

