6.6.2 Not Permitted

Strong CYP3A inducers should be avoided during treatment with ixazomib and/or ibrutinib:

- Avoid concomitant administration with strong CYP3A inducers (such as rifampin, phenytoin, carbamazepine, and St. John's Wort).

Systemic treatment with any of the above metabolizing enzyme inducers should be avoided, unless there is no appropriate alternative medication for the patient's use (Rationale: If there were to be a drug-drug interaction with an inducer, ixazomib and/or ibrutinib exposure would be decreased; therefore, there would be a reduced chance of an AE. However, there may be less chance for an antitumor effect, but that is not an absolute reason to be taken off ixazomib and/or ibrutinib).

Strong or moderate CYP3A inhibitors should be avoided during treatment with ibrutinib:

- Concomitant use of strong CYP3A inhibitors which would be taken chronically (e.g., ritonavir, indinavir, nelfinavir, saquinavir, boceprevir, telaprevir, nefazodone) is not recommended.
- For strong CYP3A inhibitors used short-term (e.g., antifungals and antibiotics for 7 days or less, e.g., ketoconazole, itraconazole, voriconazole, posaconazole,

clarithromycin, telithromycin) consider interrupting ibrutinib therapy during the duration of inhibitor use.

- Reduce ibrutinib to 140 mg if a moderate CYP3A inhibitor must be used (e.g., fluconazole, darunavir, erythromycin, diltiazem, atazanavir, aprepitant, amprenavir, fosamprenavir, crizotinib, imatinib, verapamil, and ciprofloxacin).
- Avoid grapefruit and Seville oranges during ibrutinib treatment, as these contain moderate inhibitors of CYP3A.

Patients taking concomitant strong or moderate CYP3A4 inhibitors should be monitored more closely for signs of ibrutinib toxicity.

The following procedures are prohibited during the study.

- Any antineoplastic treatment with activity against lymphoma, other than study drugs. This includes corticosteroids which should not be used with the intent to treat the underlying lymphoma for a patient who has initiated study therapy. Corticosteroid use as an anti-emetic or for other non-malignant etiologies may be used but should be limited to the smallest dose and duration required and should be documented.
- Radiation therapy (note that, in general, the requirement for local radiation therapy indicates disease progression).
- Platelet transfusions to help patients meet eligibility criteria are not allowed within 3 days prior to study drug dosing for any dosing day.

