9.1 Scheduled Restaging Studies

All patients shall complete a PET/CT at the time of study enrollment. Thereafter, restaging shall include CT chest/abdomen/pelvis after cycles 3, 6, 9, and 12, and then every 6 months while on study therapy. PET/CT or MRI may be substituted for CT at the discretion of the treating investigator, especially in cases where lesions are not readily noted on CT. Patients who discontinue study therapy for reasons other than disease progression shall have CT's performed every 6 months until progression and/or initiation of a new therapy.

All patients with suspected CR based on routine restaging should have a PET/CT performed to confirm CR.

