9.6 Criteria for PET/CT Reporting

Patients who undergo PET/CT as part of their interim, on-treatment, and end of treatment staging assessments should be assessed according to the following scoring system.

1. No uptake above background.
2. Uptake \leq mediastinum.
3. Uptake $>$ mediastinum but \leq liver.
4. Uptake moderately greater than liver.
5. Uptake markedly higher than liver and/or new lesions.

X New areas of uptake unlikely to be related to lymphoma.

For further information regarding the Deauville scoring system, please refer to Barrington et al, J Clin Oncol 2014³⁵.

10. Study Parameters

1. All pre-study scans should be done \leq 4 weeks prior to registration.
2. All other pre-study assessments should be done \leq 2 weeks prior to registration.

Procedures	Screening	Cycle 1* (1 cycle=28 Days)				Cycle 2-Cycle 6*				Cycle 7 and Subsequent Cycles ^{12*}	Every 3 Cycles*	Off Treatment ¹⁴	Follow- Up ¹⁶
		Day 1 +/- 1 day	Day 8 +/- 1 day	Day 15 +/- 1 day	Day 22	Day 1 +/- 3 days	Day 8 +/- 3 days	Day 15 +/- 3 days	Day 22 BREAK				
Written Informed Consent	X												
Disease Characteristics ¹	X												
Medical/Surgical History	X												
Assessment of Baseline Signs & Symptoms	X												
Height	X												
Physical Exam including Weight	X	X		X		X				X ¹²		X	
Vital Signs (Temperature, Pulse, Blood Pressure)	X	X		X		X				X ¹²		X	
Performance Status	X	X				X				X ¹²		X	
CBC/Differential/Platelets ²	X	X		X	X	X ²		X ²		X ²		X	
Chemistry ³	X	X		X		X ³				X ³		X	
PT/INR	X												
Lactate Dehydrogenase (LDH)	X												
Vitamin D Level ⁴	X												
Peripheral Blood Flow Cytometry	X												
Serum Pregnancy Test ⁵	X												
PET/CT	X												
Chest/Abdomen/Pelvic MRI or CT ⁶										X ¹³		X	
Bone Marrow Aspirate and Biopsy ⁷	X											X ⁷	

Procedures	Screening	Cycle 1* (1 cycle=28 Days)				Cycle 2-Cycle 6*				Cycle 7 and Subsequent Cycles ^{12*}	Every 3 Cycles*	Off Treatment ¹⁴	Follow- Up ¹⁶
		Day 1 +/- 1 day	Day 8 +/- 1 day	Day 15 +/- 1 day	Day 22	Day 1 +/- 3 days	Day 8 +/- 3 days	Day 15 +/- 3 days	Day 22 BREAK				
Bone Marrow Conventional Cytogenetics and FISH ⁸	X												
Pathology Review with Ki67 Assessment ⁹	X												
Research Specimens ¹⁰		X ¹⁰									X ¹⁰	X ¹⁰	
Treatment Administration ¹¹		X	X ¹¹	X		X ¹¹	X ¹¹	X ¹¹		X ¹¹			
Concomitant Medication Review	X	X		X		X				X ¹²		X	
Adverse Events Assessment		X		X		X				X ¹²		X ¹⁵	
Survival Status													X

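### The baseline scan may precede the end of prior lymphoma therapy by up to 14 days, so regression from that therapy can be credited to the combination: directly in ORR, and in the CR rate only through who qualifies as measurable

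*Protocol*

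**What the plan says.** Five places in the protocol bear on this.

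- **Washout (criterion 3.10).** For systemic therapy: "Patients must not have received systemic treatment for MCL for at least 14 days prior to enrollment, except for steroids". The exception covers "steroids which may be used to manage acute symptoms related to disease up to 48 hours prior to starting study therapy". For radiation: "Radiation therapy must be concluded at least 14 days prior to enrollment".
- **Baseline scan.** Section 10 opens with "All pre-study scans should be done" no more than 4 weeks before registration. Section 9.1 words it differently: "All patients shall complete a PET/CT at the time of study enrollment".
- **Entry disease status.** Criterion 3.2: "Patients must have been refractory to and/or relapsed/progressed after at least 1 prior therapy". Criterion 3.1 asks for relapsed or refractory disease. Criterion 3.14 asks for measurable disease on imaging. None of these ties the finding to the most recent therapy, or to a time after it.
- **Start of treatment (synopsis and Section 4.3).** Within 10 working days of registration.
- **Response (Sections 9.2, 9.3 and 12.2.1).** CR is defined by an end state. PR is a fall in SPD of at least 50%, or reduced uptake compared with baseline. The primary test in Cohort A rejects a 21% CR rate if 10 or more of 31 patients reach CR.

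**The concern.** In a single-arm trial the baseline scan is the only separation between what earlier treatment did and what the study drugs did. If the scan may come first and prior therapy may continue after it, later regression has no other owner in the analysis and is credited to ixazomib plus ibrutinib. No control arm shares the effect. The protocol itself treats steroids as active against the disease: Section 6.6.2 bars antineoplastic treatment during the study and adds "This includes corticosteroids which should not be used with the intent to treat the underlying lymphoma". The same exposure is left open between the baseline scan and the first dose.

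At stake are the ORR and, by a narrower route, the primary CR rate, whose decision rule has little room for stray responders.

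**Working it through.** **1. The windows.** Inputs: scan up to 28 days before registration (Section 10); systemic therapy and radiation until 14 days before enrolment, and steroids until 48 hours before treatment (criterion 3.10); treatment within 10 working days of registration, about 14 calendar days. Enrolment and registration are taken as the same day.

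- Scan to end of prior systemic therapy or radiation: 28 − 14 = 14 days at most.
- Scan to first study dose: 28 + 14 = 42 days at most.
- Scan to last permitted steroid dose: 42 − 2 = 40 days at most.

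These are calendar limits, not expected values.

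**2. Does any passage close the gap?** Section 9.1 gives a time for the PET/CT but no order relative to prior therapy. Criteria 3.1 and 3.2 do not require failure of the most recent therapy. Criterion 3.14 does not require measurable disease after the last therapy, or outside an irradiated field. No repeat scan is required before treatment; first restaging is after cycle 3. The gap stays open.

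**3. Route to each endpoint.**

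- PR and ORR: the comparison is with baseline, so regression after an early scan counts directly.
- CR: nodes of 1.5 cm or less, or Deauville 1 to 3, with no new lesions and clear marrow. The timing of the baseline scan does not change whether a later scan meets this. It matters only because an early scan can admit, as measurable, a patient whose disease was already clearing.
- PFS: on CT, progression is measured from nadir (Section 9.5). A lower nadir can bring progression forward, so the direction is unclear and no claim is made.

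**4. The design as stated.** Exact binomial, n = 31, reject if X ≥ 10:

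- P(X ≥ 10 | 0.21) = 0.0975, within the stated 10%.
- P(X ≥ 10 | 0.40) = 0.857, the stated 86%.
- A cut-off of 9 would give 0.187, so 10 is the smallest that holds 10%.

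The design figures reproduce and are not in question.

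**5. Sensitivity to carry-over (assumed, since the protocol gives no rate).** Let k of the 31 be carry-over CRs and the other 31 − k have the null rate. The rejection probability is P(Bin(31 − k, 0.21) ≥ 10 − k).

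| k | Expression | Probability |
|---|---|---|
| 0 | P(Bin(31, 0.21) ≥ 10) | 0.098 |
| 1 | P(Bin(30, 0.21) ≥ 9) | 0.161 |
| 2 | P(Bin(29, 0.21) ≥ 8) | 0.252 |
| 3 | P(Bin(28, 0.21) ≥ 7) | 0.371 |

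Alternatively, let each patient independently have a carry-over CR with probability c, so that p = 0.21 + 0.79c. For c = 2%, 5% and 10%, p = 0.226, 0.250 and 0.289, and P(X ≥ 10) = 0.142, 0.227 and 0.405.

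**The case against.** The case for leaving the text alone has several parts.

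- **Section 9.1 already places the scan at enrolment.** With a 14-day washout, that would put it after therapy, and Section 10 would be only an outer limit. This is a fair reading, but Section 10 is the schedule and it expressly permits 4 weeks. The two need reconciling.
- **CR is absolute.** A reader might infer that shrinkage since the baseline scan counts towards the primary endpoint as it does for PR. Section 9.2 does not support that; only the eligibility route remains. This part of the objection stands.
- **The bias is not only favourable.** A reader might infer that every response and survival endpoint is flattered. Section 9.5 does not support that for PFS. Moreover, disease growing untreated after an early scan makes a 50% fall harder to reach. This also stands; the concern is carry-over into CR and ORR, not the net sign over all patients.
- **The error rates can be overstated.** Keeping all 31 patients at 21% and adding one or two CRs on top gives P(X ≥ 9) = 18.7% and P(X ≥ 8) = 31.9%. That supposes each carry-over CR falls in a patient certain not to respond otherwise. Fixing those patients within the 31 gives 16.1% and 25.2%.
- **The worst case stacks several limits.** The steroid exception is confined to acute disease symptoms. First restaging is about 84 days (3 × 28) into treatment, when a short steroid effect may have faded. Suspected CR should be confirmed by PET/CT. All of this limits the likely size.
- **The historical 21% may contain similar carry-over.** The scan and washout rules of that ibrutinib study are not in the protocol, so this cannot be settled.

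**Conclusion.** The concern holds in limited form. The protocol permits a baseline scan up to 14 days before the end of prior systemic therapy or radiation, and up to about 40 days before the last permitted steroid dose. Nothing in it sets the order. ORR is exposed directly; the CR rate is exposed only through entry on measurable disease that was already regressing.

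How often this happens is unknown, and the text shows only that it can. If it produced 1 to 3 CRs among the 31 patients, with all others at the null rate, the false-positive probability would be 16.1% to 37.1% instead of 9.8%. Those figures are conditional on such CRs occurring and do not estimate the trial's actual error rate. The point is a worthwhile, low-cost tightening rather than a flaw in the 31-patient design.

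**What to change.** - **Protocol text.** Align Sections 9.1 and 10. Require the baseline PET/CT, and the measurable disease shown for criterion 3.14, to be obtained after the last prior systemic anti-lymphoma dose and the last radiation fraction, still within 4 weeks of registration. State that a lesion irradiated without later progression is not a target lesion.
- **Patients already enrolled.** Compare the date of last therapy, already on the checklist at criterion 3.2, with the baseline scan date. As a sensitivity analysis only, report the CR rate and ORR with responders whose scan preceded the end of prior therapy counted as non-responders. List responders who received steroids between the scan and the first dose.

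**Cost.** The number of scans, the sample size, the cut-off of 10 and the power of 0.857 are unchanged. Some patients would be scanned one to two weeks later. The sensitivity analysis may discount some genuine responses. Regression that continues after a scan taken once therapy has ended would still be credited to the study drugs, so the change reduces carry-over without eliminating it.
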